3.4.2.1. Local Reactions

Local reactions for Cohorts 2, 3, and 4 reported in the e-diary are redness, swelling, and tenderness.

Redness and swelling will be measured and recorded in measuring device units (range: 1 to 14) for 7 days following vaccination (Day 1 to 7), and then categorized using the scale shown in Table 3 below. The measurements will then be recorded in the e-diary.

A measuring device will be given to the caregiver(s) with instructions for measuring any redness or swelling at the injection site. Each unit is equivalent to 0.5 cm. The caregiver(s) will be asked to measure and to report the largest diameters of a local reaction. In case a measurement is between 2 values, the higher value should be reported. At the time of entry into the e-diary, the caregiver(s) should record the maximum severity of the reaction since the previous entry into the e-diary.

Absent	No redness or swelling present (0 units)
Mild	0.5 to 2.0 cm (1 to 4 units)
Moderate	2.5 to 7.0 cm (5 to 14 units)
Severe	>7.0 cm (>14 units)

Table 3. Redness and Swelling

The caregiver will be asked to assess whether tenderness is present at the investigational product (13vPnC or Hib vaccine) injection site and grade it according to the scale shown in Table 4. The caregiver will then record the assessment in the e-diary. For events that were ongoing on the last day that the e-diary was completed, the end date will be collected in the case report form (CRF).

Table 4. Tenderness

Absent	No discernible tenderness
Present	Tenderness present
Significant	Tenderness interfering with limb movement

Although the e-diary was designed in such a way that the parent could not skip a question without answering it, the possibility of conflicting responses still exists. For redness and swelling, device units could be recorded with no or missing answer to the root question; or, redness/swelling could be recorded as yes with a measuring device unit of zero (if defaulted by database). The combination of no with a device unit recorded will result in the answer to the root question being considered yes. The combination of yes with a device equal to 0 will result in the measuring device unit being considered as ">0". A missing value for the root question with a positive value for measuring device units will result in the answer to the root question being considered yes. These rules are summarized in Table 5 below.

Re	eported Response	Recoded	l Response
Present	Measuring Device Units	Present	Measuring Device Units
Missing	Missing	Missing	Missing
Missing	0	Missing	Missing
Missing	1-14	Yes	1-14
Missing	14+	Yes	14+
Yes	Missing	Yes	Missing
Yes	0	Yes	>0
Yes	1-14	Yes	1-14
Yes	14+	Yes	14+
No	Missing	No	Missing
No	0	No	Missing
No	1-14	Yes	1-14
No	14+	Yes	14+

Table 5.Data Conventions for Redness and Swelling in the Presence of Inconsistent
or Missing Responses

Redness and swelling will be further categorized according to the following scale based on the recoded responses:

- = •, if both variables (presence/absence and device units) are missing or otherwise unavailable, or if present and device units is missing;
- = 0 (absent) if not present and device unit is missing;
- = 1 (mild), if present and area is 0.5 to 2.0 cm (1 to 4 device units), or if present and measuring device units are ">0";
- = 2 (moderate), if present and area is >2.0 to 7.0 cm (5 to 14 device units);
- = 3 (severe), if present and area is >7.0 cm (>14 device units).

In addition, the maximum diameter of the affected area for redness and swelling will be determined. The maximum diameter will be derived as follows:

- = xx (maximum actual value), if present on at least 1 day in the required interval and measuring device units >0;
- = •, if values are a mixture of absent and missing for required days in the interval;
- = 0, if all values are absent for all required days in the interval.

For the purpose of creating an indicator variable for tenderness on each day, the following algorithm will be used:

- = •, if tenderness is missing;
- = 0 (absent), if tenderness is recorded as none discernible;
- = 1 (present), if tenderness is recorded as present;
- = 2 (significant), if tenderness is recorded as interferes with limb movement.

For the local reactions, 3 more derivations are required: whether or not a specific reaction occurred on "any day", whether or not the subject experienced "any local reaction" on a given day, and whether or not the subject experienced "any local reaction" on "any day".

For the occurrence of a specific reaction on "any day", the following algorithm is used and is summarized in Table 6:

- = 1 (yes), if the subject reports the specified reaction as yes (or present) on any day in the required interval;
- = 0 (no), if the subject reports the specified reaction as no (or absent) for all days in the required interval;
- = •, if the subject reports the specified reaction as a combination of no and missing for all days in the required interval.

Table 6.Derivation of "Each Day" and "Any Day" for Local Reactions in the
Presence of Missing Values

Subject	Day	Response	Each Day	Any Day
1	1	missing	missing	
	2	no	No	
	3	yes	Yes	
	4	no	No	yes
2	1	no	No	
	2	yes	Yes	
	3	missing	missing	
	4	no	No	yes
3	1	no	No	
	2	missing	missing	
	3	no	No	
	4	no	No	missing
4	1	no	No	
	2	no	No	
	3	no	No	
	4	no	No	no

For "any local reaction" on a given day, a similar rule applies:

- = 1 (yes), if the subject reports any reaction as yes (or present) on the given day in the required interval;
- = 0 (no), if the subject reports all reactions as no (or absent) on the given day in the required interval;
- = •, if the subject reports all reactions as a combination of no and missing on the given day in the required interval.

For "any local reaction on any day", a similar rule applies:

- = 1 (yes), if the subject reports any reaction as yes (or present) on any day in the required interval;
- = 0 (no), if the subject reports all reactions as no (or absent) for all days in the required interval;
- = •, if the subject reports all reactions as a combination of no and missing.

In summarizing local reactions (over all expected days), the derivation of "any reaction" in the presence of missing values is depicted in Table 7.

Table 7.Derivation of Any Reaction for Local Reactions in the Presence of Missing
Values

Number of Reactions Reported	Number of Missing Values	Summary Value
One or more	None	Reaction
One or more	One or more	Reaction
None	None	No Reaction
None	One or more	Missing

The duration of each reaction will be calculated in days from start of first reported reaction to resolution of last reported reaction, inclusive. Resolution information is the last day on which the report was recorded in the e-diary, or, the date the reaction ended if it continued beyond day 7 (or the last record in the e-diary if before day 7). If there is no known date the reaction ended, then duration will be missing. Subjects with no reported reaction have no duration because it is not applicable.

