3.1.2. Primary Safety Endpoints

- The incidence of local reactions and systemic events (including the use of antipyretic medication) in the 7 days after each vaccination (13vPnC or Hib) in Cohorts 2, 3 and 4.
- The incidence of AEs from the signing of the informed consent document (ICD) to 1 month after the last vaccination (13vPnC or Hib) in Cohort 2, 3 and 4.
- The incidence of newly diagnosed chronic medical conditions from 1 month after the last study vaccination (13vPnC or Hib) to 6 months after the last study vaccination in Cohort 2, 3 and 4.

PFIZER CONFIDENTIAL Page 8

[figure not shown]
• The incidence of serious adverse events (SAEs) from the signing of the ICD to 6 months after the last study vaccination (13vPnC or Hib) in Cohort 2, 3 and 4.

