3.5. Study Conduct

3.5.1. E-Diary Completion

An e-diary will be considered transmitted if any data for the local reactions and the systemic events are present on any day. If all data are missing for all items on the e-diary for all 7 days following vaccination, then the e-diary will be considered not transmitted.

For transmitted e-diaries, the following variables will be defined: "Day 1," "Day 2," "Day 3," "Day 4," "Day 5," "Day 6," "Day 7," "Day 1 – Day 7".

An e-diary will be considered completed if all expected data for all 7 days are available (ie, not missing) and data are valid. Otherwise, the e-diary will be considered incomplete.

For any given day, an e-diary will be considered complete if all expected data are available.

For completed e-diaries, the following variables will be defined: "Day 1," "Day 2," "Day 3," "Day 4," "Day 5," "Day 6," "Day 7," "Day 1 – Day 7".

For e-diaries that are incomplete, an indicator variable for the percentage of days without data will be derived as follows:

- = 1, if data have been transmitted, and are complete for 7 days (100%);
- = 2, if data have been transmitted, and are complete for 6 days (\geq 75% to <100%);
- = 3, if data have been transmitted, and are complete for 4 or 5 days (\geq 50% to <75%);
- = 4, if data have been transmitted, and are complete for 2 or 3 days ($\geq 25\%$ to <50%);
- = 5, if data have been transmitted, and are complete for 0 or 1 day (<25%).

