5.3.2. Safety Data

Handling of missing information related to safety data, such as missing or partially missing date, will be in accordance with Pfizer reporting standards.

For derived variables in reactogenicity data, if any day of the 7-day e-diary is available, the "Day 1 - Day 7" data will be considered as nonmissing for analyses after each dose of Cohorts 2, 3 and 4. The proportion of subjects with missing reactogenicity data will also be summarized by each dose in Cohort 2, 3, and 4 for each vaccine group. The denominator will be the number of subjects who receive the scheduled vaccination.

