6.4.2. Reactogenicity Data

The derived endpoints (Section 3.4.2) for each local reaction, systemic event, and use of antipyretic/pain medication to prevent or treat symptoms will be summarized.

The presence and maximum severity of the local reaction and systemic event at "any day (Day 1 - Day 7)" for each vaccination (13vPnC or Hib) following each dose in Cohort 2, 3, 4 will be summarized by proportions of subjects with the associated 95% Clopper-Pearson CIs.

The presence of each local reaction and systemic event on any day (Day 1-7), any local reaction on any day (Day 1-7), maximum severity of each local reaction and systemic event on any day (Day 1-7) following any vaccination in Cohort 2, 3, 4 will also be summarized by proportions of subjects with associated Clopper-Pearson CIs. For local reactions, systemic events, and use of antipyretic/pain medication to prevent or treat symptoms, descriptive summary statistics of the maximum duration of the event will be provided.

For the onset of local reactions, systemic events, and use of antipyretic/pain medication to prevent or treat symptoms, descriptive summary statistics of the onset day will be provided.

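### SAP 3.4.2.1 and SAP 5.3.2 treat a partial e-diary with no recorded reaction differently, and SAP 6.4.2 does not say which rule or denominator applies to the primary reactogenicity incidences

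*SAP*

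**What the plan says.** The endpoint is a primary safety endpoint for Cohorts 2 to 4 (SAP 3.1.2): "The incidence of local reactions and systemic events (including the use of antipyretic medication) in the 7 days after each vaccination".

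- **SAP 3.4.2.1.** A specific reaction on any day is 'no' only if 'no' is recorded for every day. It is missing "if the subject reports the specified reaction as a combination of no and missing for all days in the required interval". Table 6, subject 3 (no, missing, no, no) is shown as missing. The last row of Table 7 (no reaction reported, one or more missing values) is also missing, and Table 7 is introduced as a rule for the summaries: "In summarizing local reactions (over all expected days), the derivation of 'any reaction' in the presence of missing values is depicted in Table 7". SAP 3.4.2.2 carries these derivations to fever, other systemic events and antipyretic use.
- **SAP 5.3.2.** "For derived variables in reactogenicity data, if any day of the 7-day e-diary is available", the data for Day 1 to Day 7 count as nonmissing for analyses after each dose. The section's only denominator, subjects who receive the scheduled vaccination, follows the sentence on the proportion with missing reactogenicity data.
- **SAP 6.4.2.** It reports "The presence and maximum severity of the local reaction and systemic event at 'any day (Day 1 - Day 7)' for each vaccination" as proportions with Clopper-Pearson intervals. It names no denominator and does not choose between the two rules.

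Partial diaries are foreseen. Protocol 7.1 allows entry only within a fixed time window, and SAP 3.5.1 grades incomplete diaries by the number of days completed.

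**The concern.** The same diary, with some 'no' days, some missing days and no reaction, is missing under one section and nonmissing under the other, and no section takes precedence. Two programmers could produce different Ns and different rates for a primary safety endpoint. The proportion with missing reactogenicity data could change too.

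The 3.4.2.1 rule also selects on the outcome. A partial diary that shows a reaction stays in the denominator, and one that shows none leaves it. If days are missing at random, this pushes the incidence upward.

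**Working it through.** **1. The rules on the SAP's own example.** Applied to the four subjects of Table 6, the 3.4.2.1 algorithm gives yes, yes, missing, no, exactly as printed. The 5.3.2 rule makes all four nonmissing. If nonmissing without a reaction is read as 'no', it gives yes, yes, no, no. The rules part only at subject 3. A diary with one 'no' day and six missing days is likewise missing under one and 'no' under the other.

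**2. Size when days are missing at random.** The documents give no completion or reaction rate, so these inputs are assumed: true seven-day incidence p = 0.20; partial-diary fraction f = 0.05, 0.10 or 0.20; onset on day 1 or 2; duration 1, 2 or 3 days with equal probability; m of 7 days missing at random. Let q be the probability that a partial diary still records a reaction that occurred.

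- Recorded yes = p[1 − f(1 − q)]
- Dropped under 3.4.2.1 = f[(1 − p) + p(1 − q)]
- Rate under 3.4.2.1 = yes / (1 − dropped)
- Rate under 5.3.2 read as 'no' = yes

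The first rate divides the same numerator by a number no greater than 1, so it is never below the second.

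For m = 1, only a one-day reaction can be lost: q = 1 − (1/3)(1/7) = 0.952. With f = 0.20, yes = 0.20(1 − 0.20 × 0.048) = 0.198, dropped = 0.20(0.80 + 0.20 × 0.048) = 0.162, and the 3.4.2.1 rate is 0.198/0.838 = 23.6%.

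| Partial diaries (m = 1) | 3.4.2.1 | 5.3.2 as 'no' |
|---|---|---|
| 5% | 20.8% | 20.0% |
| 10% | 21.7% | 19.9% |
| 20% | 23.6% | 19.8% |

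**3. Local reactions, with the recording instruction.** SAP 3.4.2.1 asks the caregiver to enter the maximum severity since the previous entry. If this is followed, any entry on or after onset captures the reaction. With 1 to 5 missing days at least two days are observed, one of them day 2 or later, so q = 1. With six missing, capture fails only if onset is on day 2 and the observed day is day 1: q = 1 − (1/2)(1/7) = 0.929. At f = 0.20:

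- m = 1 to 5: 5.3.2 as 'no' gives 20.0%; 3.4.2.1 gives 0.20/(1 − 0.16) = 23.8%.
- m = 6: yes = 0.20(1 − 0.20 × 0.071) = 19.7%; 3.4.2.1 gives 0.197/0.837 = 23.5%.

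**4. Events without that instruction (temperature, other systemic events).** Using the formulas of step 2 at f = 0.20:

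| Missing days | q | 3.4.2.1 | 5.3.2 as 'no' | Under-count of 5.3.2 as 'no' |
|---|---|---|---|---|
| 4 | 0.676 | 22.6% | 18.7% | 1.3 points |
| 5 | 0.508 | 22.0% | 18.0% | 2.0 points |
| 6 | 0.286 | 21.1% | 17.1% | 2.9 points |

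Here 5.3.2 as 'no' is closer to 20% with four missing days, the two are about equally far off with five, and 3.4.2.1 is closer with six.

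**5. At the planned arm size.** Protocol Table 15 plans 118 subjects on 13vPnC per cohort. With 24 reactions, 24/118 = 20.3% (exact 95% CI 13.5 to 28.7). Dropping about 5, 10 or 20% of the 94 no-reaction diaries (5, 9 or 19) gives 24/113 = 21.2%, 24/109 = 22.0% or 24/99 = 24.2%. All lie within that interval.

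**The case against.** The strongest reply is that 5.3.2 is only a diary-level test. SAP 3.5.1 uses the same Day 1 to Day 7 label for completion and a similar any-data test: "An e-diary will be considered transmitted if any data for the local reactions and the systemic events are present on any day". The rest of the 5.3.2 paragraph is about tabulating missing data. This reading is possible, but the SAP does not state it, and the reference to derived variables and to analyses counts against it. The text needs correcting under either reading.

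It is also true that 5.3.2 never says a nonmissing partial diary without a reaction counts as 'no'. That step is an inference, and every 5.3.2 figure above depends on it.

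The consequence is limited. SAP 5.1 sets no decision rule, SAP 5.2 shows n and N, and SAP 6.3.1.3 tabulates diary completion. That stands, but N alone does not tell a reader which rule was planned.

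A reader might infer more than the documents support:

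- **That the two rules are equally biased in opposite directions.** For local reactions the recording instruction, if followed, nearly removes the under-count, so 3.4.2.1 is the further from the truth in every case of step 3.
- **That the 13vPnC versus Hib comparison is distorted.** A material distortion would need clearly different rates of partial diaries between the arms. The study is open-label, so this is conceivable, but nothing in the documents indicates it.
- **That 5.3.2 already fixes an incidence denominator.** Its one denominator most naturally belongs to the missing-data proportion.

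**Conclusion.** The point holds as a conflict in the SAP's wording that leaves the value of a partial no-reaction diary and the incidence denominator undefined for a primary safety endpoint. The conflict extends to fever, other systemic events and antipyretic use.

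Under the stated assumptions, with one random missing day, the 3.4.2.1 rule overstates a true 20% by 0.8 to 3.6 points as partial diaries rise from 5 to 20%. For local reactions, 5.3.2 read as 'no' is off by at most 0.3 points at 20% partial diaries if caregivers follow the recording instruction. Under-counts of 1.3 to 2.9 points could arise only for events without that instruction and with four to six days missing.

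These sizes depend on an unknown completion rate and on the assumed timing. The documents do not support a claim that any conclusion of the study would change. The correction is still worth making, because 3.4.2.1 as written selects on the outcome.

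**What to change.** - Reconcile SAP 3.4.2.1, Table 6 (subject 3), the last row of Table 7, 5.3.2 and 6.4.2 to one rule for all any-day reactogenicity variables.
- State the value given to a partial diary with no recorded reaction, and state the incidence denominator explicitly. A denominator that does not depend on the outcome, such as subjects with at least one diary day after that dose, is the less biased choice, at least for local reactions.
- SAP Section 2 says the primary-report analyses had already been performed, so a new main rule would be chosen after results exist. State which rule the primary report used, keep it in the supplemental report for comparability, and show the other rule as a sensitivity analysis in both.

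The cost is SAP wording, one derivation and one extra table. The drawback of the at-least-one-day denominator with partial diaries counted as 'no' is some under-counting of systemic events whose only event day is missing; the sensitivity analysis would show how much this could matter.

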7.2. Local Reactions

Cohorts 2, 3 and 4: Local reactions (redness, swelling, and tenderness) at the site of the investigational product (13vPnC or Hib vaccine) injection will be monitored daily for 7 days (day 1 to day 7) after each vaccination. An end date will be captured for all reactions either via the e-diary or CRF as applicable.

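### Reactions whose end date is never obtained drop out of the duration summaries, although the diary gives a known minimum duration; keep them as censored values and count them

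*SAP*

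**What the plan says.** SAP section 3.4.2.1 defines duration as a span, running "from start of first reported reaction to resolution of last reported reaction, inclusive". Resolution is the last diary day with a report or, for a reaction that outlasts the diary, "the date the reaction ended if it continued beyond day 7". The same applies when the last diary record falls before day 7. The closing rule is "If there is no known date the reaction ended, then duration will be missing".

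SAP sections 3.4.2.2.1 (fever) and 3.4.2.2.3 (antipyretic medication) take over this derivation. SAP section 6.4.2 then states that, for local reactions, systemic events and antipyretic use, "descriptive summary statistics of the maximum duration of the event will be provided".

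End dates are meant to be collected. Protocol section 7.2 says of local reactions: "An end date will be captured for all reactions either via the e-diary or CRF as applicable". SAP section 3.4.2.1 repeats this for tenderness: "For events that were ongoing on the last day that the e-diary was completed, the end date will be collected in the case report form". Protocol sections 7.3.1 to 7.3.3 make similar provision for fever, other systemic events and antipyretic use.

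On missing data in general, SAP section 5.3.2 says: "Handling of missing information related to safety data, such as missing or partially missing date, will be in accordance with Pfizer reporting standards". Those standards are not reproduced in the documents.

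**The concern.** When a caregiver has reported a reaction up to the last diary entry and nobody later records when it stopped, the true duration is unknown but its minimum is not. The rule treats this the same as having no information. The exclusion is informative, because a reaction leaves the summary precisely because it had not resolved when last observed. It also sits badly with SAP section 5.3, whose general principle is that available values stay in the analysis.

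At stake is a descriptive safety statement: how long reactions, fever and antipyretic use last, and the longest duration seen. The loss would also be hard to see. The missing-data summary in SAP section 5.3.2 treats the seven-day period as nonmissing once any single diary day is available, so it would not pick up missing durations.

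**Working it through.** The documents state no figure for duration, so there is no figure of the plan to reproduce.

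**Step 1: which reactions are lost.**

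| Situation | Duration under SAP 3.4.2.1 |
|---|---|
| Last report within the diary, reaction over | Calculated |
| Continues past day 7 or past the last diary record, end date recorded | Calculated to the actual end date, no cap at day 7 |
| Continues past day 7 or past the last diary record, end date never obtained | Missing |

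Only the third row is lost.

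**Step 2: what is known for that row.** Minimum duration = last day known present − first reported day + 1.
- Onset day 1, present on day 7: 7 − 1 + 1 = at least 7 days.
- Onset day 5, present on day 7: 7 − 5 + 1 = at least 3 days.
- Onset day 7: 7 − 7 + 1 = at least 1 day.

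The minimum can be short. It should therefore not be averaged in as if it were an exact duration; it is a censored value.

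**Step 3: possible size.** From the documents: 118 subjects planned on 13vPnC in each of Cohorts 2 to 4 (Protocol Table 15). Assumptions, not in the documents: 30% react (118 × 0.30 ≈ 35 reactors); mean 2 days if resolved by day 7 and 10 days if ongoing; a share g of reactions ongoing past day 7; a share u of those with no end date.

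- True mean = (1 − g) × 2 + g × 10
- Reported mean = [(1 − g) × 2 + g(1 − u) × 10] / [(1 − g) + g(1 − u)]
- Expected number dropped = 35 × g × u

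| g | u | True mean (days) | Reported mean (days) | Bias (days) | Dropped |
|---|---|---|---|---|---|
| any | 0% | – | equal to true | 0 | 0 |
| 2% | 10% | 2.16 | 2.14 | −0.02 | 0.07 |
| 5% | 25% | 2.40 | 2.30 | −0.10 | 0.44 |
| 5% | 100% | 2.40 | 2.00 | −0.40 | 1.75 |
| 10% | 100% | 2.80 | 2.00 | −0.80 | 3.50 |

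Worked for g = 5%, u = 25%: true mean 0.95 × 2 + 0.05 × 10 = 2.40; reported mean (1.90 + 0.375) / (0.95 + 0.0375) = 2.275 / 0.9875 = 2.30; dropped 35 × 0.05 × 0.25 = 0.44.

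The reported maximum is more fragile than the mean, since it can change when a single long reaction is dropped.

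**Step 4: can the loss be seen?** SAP section 5.2 gives n for continuous variables, so a reader could try subtracting the n of a duration table from the number of reactors. That is indirect, and no planned table reports the count itself.

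**The case against.** The strongest reply is that this is a fallback rule for cases that should hardly occur. End dates are planned for every reaction, a scheduled visit follows each vaccination, and a reaction that outlasts the diary keeps its real end date without a cap. Duration is descriptive and enters no test. A reaction with an unknown end date still counts as present in the incidence tables and still contributes its maximum severity. All of this stands, and it limits the point to a minor one. It does not justify the rule for the cases that remain: the SAP foresees them and chooses to discard what is known. The reference to sponsor standards for missing dates does not settle the matter either, because section 3.4.2.1 gives its own specific rule.

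A reader might infer three stronger things, which the documents do not support:

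- *All reactions unresolved at day 7 are dropped.* They are not; see the second row of the table in the working.
- *Counting reaction-free days between reports overstates intermittent reactions.* The SAP openly defines duration as "The duration of each reaction will be calculated in days from start of first reported reaction to resolution of last reported reaction, inclusive". A first-to-last span is a coherent quantity. Preferring days present is a choice of measure and does not correct an error. The protocol's one-day criterion for fever resolution governs how long temperature is taken and does not redefine this span.
- *End dates will be captured differently by arm because the study is open-label.* After the same dose in the same cohort, both arms have the same interval to the next visit, and nothing in the documents shows different follow-up.

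**Conclusion.** The point holds in a narrow form. Reactions, fevers and antipyretic use whose end date is never obtained leave the duration summaries although a minimum is known, and no planned table reports how many. Where this occurs, the exclusion is informative and can understate both summary and maximum duration.

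The documents do not allow the size to be fixed. It is zero if end-date collection works as planned. Under the assumptions in the working, the mean is understated by 0.10 day in a moderate case, with fewer than one subject expected to be dropped, and by 0.80 day if 10% of reactions are ongoing past day 7 and none of those end dates is obtained. This is a minor reporting improvement. The primary reactogenicity endpoint (incidence within 7 days) and the severity tables do not use duration and are unaffected.

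**What to change.** In SAP section 3.4.2.1, and through it for fever and antipyretic use, replace the missing-duration rule with the following:

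- If no end date is known, treat the duration as censored at the last day the event is known to have been present.
- Show such values as ≥ x days, and include them when reporting the longest duration.
- Report the number of events with an unknown end date by vaccine group and dose.
- Do not enter the minimum as an exact value in the mean.

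A Kaplan-Meier median and a count of days present are optional additions.

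The cost is SAP wording, minor programming and a slightly less tidy descriptive table; no new data are needed. SAP section 2 already plans to repeat all analyses with the additional 280 subjects for a supplemental report, so the change could be made there.
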